12.2.11 Time to First Negative Sputum Culture

Kaplan-Meier methods will be utilized to determine the time to first sputum culture negative for MABC for the ITT Analysis Set by treatment group. Time to first negative sputum culture is defined as the number of days from the date of the first dose of test article administration to the date of the first sputum culture negative for MABC. A culture is considered negative if there is no growth in broth (ie, liquid medium) and no growth on agar plate (ie, no growth on either LJ slant or biplate) for MABC regardless of subspecies. For example, if the baseline culture grows *M. abcessus* subspecies *abcessus* and the post-baseline sample grows *M. abcessus* subspecies *massiliense*, the culture is considered positive for MABC. Subjects who died, withdrew from the study, or received alternative antibiotic therapy (not including chronic macrolides) for treatment of the NTM infection prior to sputum culture negative for MABC will be censored at the date of the death, study withdrawal, or the start date of the alternative antibiotic therapy respectively. Subjects who have a positive sputum culture through Day 84 will be censored at the date of the Day 84 visit.

The median, 25th and 75th percentile for time to first negative sputum culture will be provided with 2-sided 95% CIs for each treatment group. The probability of a negative sputum culture at Days 28, 56 and 84 will also be presented along with the 2-sided 95% CIs for each treatment group. A p-value will be determined using a stratified (by prior antibiotic use) log-rank test. Kaplan-Meier curve for time to first negative sputum culture will be provided in a figure.

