9.2 Double-blind Treatment Period

The double-blind treatment period is approximately 3 months (84 days) in duration. Subjects who meet all of the inclusion criteria and none of the exclusion criteria may be randomized.

In-clinic visits will occur at Baseline/Day 1, Day 28 (\pm 3 days), Day 56 (\pm 3 days), and Day 84/EOT (+ 5 days /- 2 days).

A tele-visit (phone call or virtual) will occur at Day 14 (\pm 2 days) to assess safety via review of AEs and concomitant medications.

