7. NOTATION OF TREATMENT GROUPS AND VISITS

Table 7.1.1 Notation of Treatment Groups

The following notation of treatment groups will be used throughout the report:

Full notation (as used in the study protocol)	Notation used throughout all tables, listings, and figures
300 mg oral omadacycline	Omadacycline 300 mg
Placebo	Placebo

Table 7.1.2 Visit Terminology

Visit	Notation used throughout all tables, listings, and figures
Screening	Screening
Day 1 Baseline	Day 1 (in Listings)/ Baseline (in Tables and Figures)
Day 14 Tele-visit (\pm 2d)	Day 14
Day 28 (\pm 3d)	Day 28

Day 56 ($\pm 3d$)	Day 56
Day 84 (+5d/-2d)	Day 84
EOT: defined as the visit occurring when subjects prematurely discontinue treatment (End of Treatment) (+5d/-2d)	EOT (shown on listings)
Day 84/EOT: defined as Day 84 for subjects who complete treatment or the visit occurring when subjects prematurely discontinue treatment (End of Treatment) (+5d/-2d)	Day 84/EOT (shown on tables)
30 Day Safety Follow-up Call (+7d)	Follow-up

EOT = end of treatment

For by visit summaries, the nominal visit will be summarized. If there is no nominal visit result, unscheduled visits that occur in the protocol defined window will be summarized instead. If multiple unscheduled visits occur in the window, the one closest to the nominal visit date will be used. For sputum cultures, if there are multiple positive cultures on the same day with different MICs to omadacycline, the culture with the highest MIC to omadacycline is used.

Study days corresponding to measurements are calculated as:

- Assessment date – date of first exposure to treatment + 1 (if assessment date is on or after the date of first exposure to treatment)
- Assessment date – date of first exposure to treatment (if assessment date is before the date of first exposure to treatment)

If the date of first exposure to treatment is missing, study days will be calculated by using the randomization date.

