10.2 Microbiology

10.2.1 Selection of Sample for Analysis

Sputum samples are collected at Screening, Baseline/Day 1, Day 28, Day 56 and Day 84/EOT. At least 2 and preferably 3 sputum samples are obtained at each time point. During Screening, samples will be collected after the subject signs the informed consent. For all subsequent visits, sputum samples should be collected on 2 to 3 consecutive days (when possible), just prior to, and up through the day of the scheduled visit.

The sputum specimens will be processed by a Central Specialty Microbiology Lab. Acid fast bacilli smear testing from sputum will be performed on all specimens received. Specimens will be further cultured in both solid and liquid media and identification of genus and species will be performed, to the subspecies level for *M. abscessus*.

In vitro susceptibility testing of antimicrobial drugs that may be used to treat *M. abscessus* pulmonary infection will be performed, and molecular characterization for select drug resistance markers will be performed.

Sputum samples noted to be of low volume will not be used for analysis unless all potential samples at a time point are of low volume. If all potential samples are of a low volume (signifying lower quality), the algorithms noted below for sample selection will be used.

For MIC susceptibility and outcome analyses of the MABC, the sample closest to but prior to the first dose of study drug (based on collection date and if on the same day as the first dose of study drug, collection date and time) which is positive for MABC is used as the baseline sample. If there are two samples positive for MABC with different subspecies, the one positive for *M. abscessus* subspecies *abscessus* is used. If multiple samples collected on the same day are positive for MABC, the sample positive for *M. abscessus* subspecies *abscessus* and with the highest MIC to omadacycline is considered the baseline sample. If the MICs are the same, the sample closest to the time of first dose of study drug based on time is used. The baseline samples for MAC and other species of mycobacterium (not *abscessus*) are defined in a similar manner and may or may not be the same sample as the one with MABC.

For post-baseline samples, a similar process is used for selecting the sample for analysis as that used for the baseline sample. The sample that is positive for MABC that is closest to the nominal/intended visit day should be selected.

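### The Kaplan-Meier culture endpoints run on actual dates with no stated link to visit windows, which can misplace in-window conversions and inflate the end of the curve

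*SAP*

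**What the plan says.** SAP 12.2.11 defines time to first negative culture as "the number of days from the date of the first dose of test article administration to the date of the first sputum culture" that shows no MABC. Non-converters are handled by this rule: "Subjects who have a positive sputum culture through Day 84 will be censored at the date of the Day 84 visit". Besides the median and quartiles, "The probability of a negative sputum culture at Days 28, 56 and 84 will also be presented along with the 2-sided 95% CIs". Section 12.2.10 (time to growth in liquid medium only) uses the same actual-date timing and Day 84 visit censoring and reports the median, quartiles and curve. It has no read-off at fixed days.

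Protocol 9.2 allows three days either side for the Day 28 and Day 56 visits, and for the last visit "Day 84/EOT (+ 5 days /- 2 days". The permitted days are therefore 25–31, 53–59 and 82–89. SAP 10.2.1 states that after Screening "sputum samples should be collected on 2 to 3 consecutive days (when possible), just prior to, and up through the day of the scheduled visit".

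SAP Section 7 has a nominal-visit rule, but its scope is limited: "For by visit summaries, the nominal visit will be summarized". Nothing extends it to the time-to-event derivations. Protocol 12.5.2.2 also defines both times by actual dates.

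**The concern.** Culture status is observed only around three visits, so the exact day of a first negative culture mostly reflects when the visit was booked. Treating that day as an exact event time has two consequences.

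- **Read-off.** A negative culture dated Days 29–31, 57–59 or 85–89 belongs to an in-window visit but falls after the day whose label it should carry. A Kaplan-Meier probability read at Day 28, 56 or 84 omits it.
- **Censoring.** A subject still positive at a Day 82 visit leaves the risk set. A subject seen on Day 88 who has converted is then counted against a depleted denominator. Both were assessed at the same planned visit, so the larger step comes from scheduling alone.

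At stake are the absolute conversion probabilities, the quartiles and the plotted curves. The study treats its p-values as descriptive, so these estimates are what readers will take from the endpoints. They may also disagree with the by-visit conversion table in Section 12.3 without explanation.

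**Working it through.** **The plan's own figure.** The plan gives none for the culture endpoints. Its only design figure is about 80% power for Day 84 clinical response (45 vs 30 subjects, 45% vs 15%). It reproduces: pooled rate (45×0.45 + 30×0.15)/75 = 0.33; null SE √(0.33×0.67×(1/45+1/30)) = 0.1108; alternative SE √(0.45×0.55/45 + 0.15×0.85/30) = 0.0987; z = (0.30 − 1.96×0.1108)/0.0987 = 0.84; power 79.9%. It has no bearing on this point.

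**Inputs from the documents.** Windows 25–31, 53–59 and 82–89 (Protocol 9.2); actual-date timing and Day 84 visit censoring (SAP 12.2.11); sputum over 2 to 3 days up to the visit (SAP 10.2.1); durations counted with +1 in SAP Appendix A, while 12.2.11 says only the number of days from first dose; 45 subjects in the larger arm (SAP Section 5).

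**Assumptions.** The documents give no conversion rate. I take a 20% chance of first conversion at each visit, with 5% as a low alternative, and no other censoring. True cumulative conversion at 20% is 20%, 1 − 0.8² = 36% and 1 − 0.8³ = 48.8%.

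**By hand: visits spread evenly over each window, culture dated on the visit day, +1 convention.**
- Day 28: four of the seven window days are on or before Day 28, so 20% × 4/7 = 11.4%.
- Day 56: 20% + (80% × 20%) × 4/7 = 29.1%.
- Day 84: 0.64 of subjects remain unconverted. One eighth of them are seen each day and leave as events or censored, so the daily hazards are 0.2/8, 0.2/7, … 0.2/1. Through Day 84 the product is 0.9750 × 0.9714 × 0.9667 = 0.9156, and 1 − 0.64 × 0.9156 = 41.4%.
- End of curve: the remaining factors 0.9600, 0.9500, 0.9333, 0.9000 and 0.8000 bring the product to 0.5611, and 1 − 0.64 × 0.5611 = 64.1% against a true 48.8%.

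With a plain date difference, one more window day counts by Day 28: 20% × 5/7 = 14.3%.

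**By simulation (45 subjects, 20% per visit, 1,500 arms per setting, +1 convention; the nominal-day row is the proposed assignment).**

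| Visit dates | First negative dated | Day 28 | Day 56 | Day 84 | Curve end |
|---|---|---|---|---|---|
| Even | visit day | 11.4% | 29.0% | 41.4% | 64.1% |
| Clustered (SD 1.5–1.8 days) | visit day | 12.5% | 30.1% | 43.7% | 67.2% |
| Even | 0–2 days before | 14.1% | 31.3% | 42.9% | 59.0% |
| Even | 2 days before | 17.0% | 33.7% | 44.8% | 54.2% |
| Clustered (SD 1.5 days) | 2 days before | 18.9% | 35.2% | 49.4% | 51.6% |
| Nominal-day assignment | – | 20.0% | 36.0% | 48.8% | 48.8% |

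With clustered visits and a plain date difference, Day 84 reads about 51–52%, above the truth.

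**Quartiles.** With cultures on the visit day or 0–2 days before it, the curve reached 50% in about 75–86% of simulated arms, although at least half the subjects had converted in only 42–44%. If every first negative is dated two days before the visit, a further run put the first figure at 56–67%.

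**Low conversion.** At 5% per visit the truth is 5.0/9.8/14.3%. The hand calculation gives 2.9/7.7/11.7% and a curve end of 21.4%. Across schedules the three read-offs stay within about 3 points, and the end is about 15–24%.

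**The case against.** The strongest reply has four parts.

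1. **The read-off is not specified.** SAP Table 7.1.2 uses Day 28 as the label for the Day 28 visit with its window, and Section 11.1 uses days 28, 56 and 84 to mean visits. A reader might infer that the SAP prescribes reading the curve at exactly those calendar days. It does not say so. This stands: the text is open, although no other reading is given for a curve whose time axis is actual days.
2. **Sputum timing reduces both errors.** Samples may precede the visit by up to two days while censoring waits for the visit date. This stands: in the most favourable schedule above, little error remains. Sites may collect fewer samples, so the result is a range.
3. **The comparison is not harmed.** A reader might infer a biased treatment test. Simulated unstratified log-rank tests (45 vs 30, 2,000 trials) gave type I error of 4.9–6.1% on actual dates and 5.3–6.0% on nominal dates, with power of 86–88% and 89% at 25% vs 8% per visit. The scheduling mechanism is the same in both arms.
4. **Other outputs cover the question.** Section 12.3 tabulates conversion by visit and at any time, which is unaffected. The endpoints are secondary and efficacy is exploratory. A curve end in the sixties is not itself a planned probability, because the read-offs stop at Day 84.

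These points limit the concern to the absolute probabilities, quartiles and plotted curves. They do not remove it.

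**Conclusion.** The point holds for those descriptive estimates. Followed as written and read at calendar days, the plan can omit in-window conversions from the Day 28 and Day 56 probabilities. At Day 84 the late-visit omission and the early censoring oppose each other, so a reader who infers a fixed direction of error there goes too far. The end of the curve was above the truth in every setting tried.

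At an assumed 20% per visit and 45 subjects (true 20/36/49%), the ranges are about 11–20%, 29–36%, 41–52% and, at the curve's end, 52–68%. The size depends on the conversion rate, the spread of visit dates, how long before the visit sputum is taken and the day-count convention. The documents settle none of these for this endpoint. The between-arm test and the Section 12.3 percentages remain usable. This is worth correcting before the curves are produced, but it does not threaten the trial's main conclusions.

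**What to change.** In SAP 12.2.10 and 12.2.11:

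- Assign cultures from visits held within their windows to nominal Day 28, 56 or 84, and censor subjects still positive at the Day 84 visit at Day 84, with events before censoring.
- Keep actual dates for early end-of-treatment cultures, out-of-window unscheduled cultures, and censoring for death, withdrawal or alternative antibiotics. Decide which came first from the actual dates before assigning nominal days.
- State that the Day 28, 56 and 84 probabilities in 12.2.11 refer to those visits.
- Run the stratified log-rank test on the same times.
- Record the change in Section 14, which currently declares none, because protocol 12.5.2.2 uses actual dates.

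The cost is a few lines of SAP text and one derivation; no new data are needed. The small downside is that event times become discrete and one derivation departs from the protocol wording. If that departure is unwelcome, keeping actual event dates, reading the curve at the window ends and using one common final censoring day would address the same two errors.

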5. DETERMINATION OF SAMPLE SIZE

As the study is exploratory with respect to determination of efficacy, the sample size determination is provided to better ensure sufficient subjects are enrolled to provide an initial assessment of efficacy rather than test a specific hypothesis. With a randomization ratio of 1.5:1, a sample size of 75 subjects (45 omadacycline and 30 placebo) will provide approximately 80% power to detect an absolute treatment difference of 30% in clinical response rate at Day 84, based on clinical response rates of 15% and 45% in the placebo and omadacycline treatment groups respectively, using a Mantel-Haenszel test with 2-sided alpha level of .05.

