10.2.2 Baseline Analyses

The following will be provided for the baseline MABC specimen:

- Baseline positive culture for MABC and by subspecies, as well as MAC and other mycobacterium.
- Distribution of the semi-quantitative score defined as follows:

Semi-quantitative culture scores	Growth in broth	Growth on agar plate	CFU/mL on an agar plate
0	-	-	0
1	+	-	0
2	+/-	+	1 - <50
3	+/-	+	50-99
4	+/-	+	100-199
5	+/-	+	200-299
6	+/-	+	≥300

- Distribution of MIC to amikacin, cefoxitin, ciprofloxacin, clarithromycin, clarithromycin-D14, clofazimine, doxycycline, imipenem, linezolid, minocycline, moxifloxacin, omadacycline, tigecycline, and trimethoprim/sulfamethoxazole
- Susceptibility profile (interpreted as resistant, susceptible and intermediate according to CLSI breakpoints) to each antibiotic with defined breakpoints
- Multidrug Resistance (MDR) defined as nonsusceptibility (MIC value interpreted as “I” or “R”) to at least one agent in three or more antimicrobial categories. Agents that do not have susceptibility interpretations i.e. those in Table 10.3.2 with ‘N/A’ will not be considered in this analysis.
- MIC range, MIC₅₀ and MIC₉₀ to omadacycline

Table 10.3.2. Antimicrobial Categories, Agents and CLSI Breakpoints

Antimicrobial Category for MDR evaluation	Antimicrobial Agent	MIC ug/mL		
		S	I	R
Aminoglycoside	Amikacin	≤16	32	≥64
Cephalosporin	Cefoxitin	≤16	32-64	≥128
Fluoroquinolone	Ciprofloxacin	≤1	2	≥4
Macrolide	Clarithromycin	≤2	4	≥8
N/A	Clofazimine	N/A	N/A	N/A
Tetracycline	Doxycycline	≤1	2-4	≥8
Carbapenem	Imipenem	≤4	8-16	≥32
Oxazolidinone	Linezolid	≤8	16	≥32

N/A	Minocycline	N/A	N/A	N/A
Fluoroquinolone	Moxifloxacin	≤1	2	≥4
Antifolate	Trimethoprim-sulfamethoxazole	≤2/38		≥4/76
N/A	Tigecycline	N/A	N/A	N/A

S=Susceptible, I=Intermediate, R=Resistant

Clinical and Laboratory Standards Institute. Performance Standards for Susceptibility Testing of Mycobacteria, Nocardia spp., and Other Aerobic Actinomycetes 1st ed. CLSI document M62. 2018. CLSI, [name].

Microbiology results will be incorporated into several of the efficacy analyses, as defined in Section 11.1.

The by-subject listings noted below will also be provided. On each listing, all samples will be presented and the baseline and post-baseline samples selected as indicated above will be indicated with a flag.

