12.2 Secondary Efficacy Analyses

Secondary efficacy endpoints will be presented as collected. Missing data will not be imputed and no adjustment for ICEs will be performed. All secondary efficacy endpoints will be analyzed using the ITT analysis set. All secondary efficacy endpoints will be summarized using descriptive statistics at each scheduled time point by treatment group as described in [Section 6](#).

The Day 84 visit time point will be presented with data as collected. The Day 84/EOT visit timepoint will include subjects who end treatment on Day 84 as well as subjects who prematurely discontinue treatment.

Secondary endpoints, where appropriate, will be analyzed using an analysis of covariance (ANCOVA) model at each visit which will include the change from baseline as the dependent variable and randomized treatment group and stratification factor (prior antibiotic treatment for MABC NTM) as fixed factors and corresponding baseline score as a covariate. Model estimated least squares (LS) means, their SDs, and 95% CIs will be presented. The difference in LS means, SDs, 95% CIs, and a p-value testing the difference between treatment group LS means will be provided.

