12.2.9 Percentage of Subjects with a Decrease in Quantitative Mycobacterial Sputum

The ninth secondary efficacy endpoint is the percentage of subjects with a decrease in quantitative mycobacterial load from the sputum culture collected at the Day 84 visit and defined as a reduction in the semi-quantitative score (as defined in Table 10.3.2) as compared to baseline. The number and percentage of subjects with a reduction in the semi-quantitative score at the Day 84 visit will be presented for the ITT analysis set by treatment group. Exact 2-sided 95% CIs for the point estimate of the percentage of subjects with a decrease in each treatment group will be determined using the Clopper-Pearson method. The odds ratio (omadacycline relative to placebo) and p-value will be calculated using Cochran-Mantel-Haenszel test, stratified by prior antibiotic use. If the sample size is too small in one of the randomization stratification subgroups such that an adjusted analysis cannot be performed, an unadjusted analysis (chi-squared or Fisher's exact test) will be used.

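### No pre-specified analysis of the three culture endpoints adjusts for baseline mycobacterial load; the gap matters most for time to first negative culture

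*SAP*

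**What the plan says.** The microbiological secondary objective rests on three endpoints.

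- **Decrease in load at Day 84 (SAP 12.2.9).** The "p-value will be calculated using Cochran-Mantel-Haenszel test, stratified by prior antibiotic use".
- **Time to growth in liquid medium only (SAP 12.2.10)** and **time to first negative culture (SAP 12.2.11).** In both, "A p-value will be determined using a stratified (by prior antibiotic use) log-rank test".

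SAP 11.3 names only the randomisation factor for adjustment. Protocol 7.7 stratifies randomisation by prior antibiotic use and by nothing else.

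Baseline load is nevertheless available. SAP 10.2.2 tabulates it for the baseline MABC specimen ("Distribution of the semi-quantitative score defined as follows"), on a scale from 0 (no growth) through 1 (broth only) to 6 (at least 300 CFU/mL). SAP 12.3 summarises CFU/mL and score by arm at baseline and each culture visit. Eligibility requires a positive Screening culture, and SAP 10.2.1 takes the last MABC-positive sample before dosing as baseline. The covariate should therefore exist for essentially every eligible subject.

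The ANCOVA endpoints in SAP 12.2 do include the "corresponding baseline score as a covariate". The culture endpoints have no equivalent.

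**The concern.** On the SAP's own scale, a subject who starts at score 1 is one category above a negative culture, while a subject at score 6 is in the open-ended top category. It is plausible that starting load influences how soon a culture turns negative. If it does, two things follow.

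First, an arm that happens to start with lower load will tend to convert sooner whatever the drug does. The SAP 12.3 tables would show such an imbalance, but no planned analysis would correct for it. SAP section 6 labels anything added after the blind is broken as post hoc and exploratory, so an adjusted estimate carries weight only if it is written down beforehand.

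Second, leaving out a prognostic covariate gives up power that the data already collected could supply.

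**Working it through.** **1. The plan's own figure.** SAP section 5 states that "a sample size of 75 subjects (45 omadacycline and 30 placebo) will provide approximately 80% power", "based on clinical response rates of 15% and 45% in the placebo and omadacycline treatment groups respectively". Pooled rate = (30 × 0.15 + 45 × 0.45)/75 = 0.33. Null SE = √(0.33 × 0.67 × (1/45 + 1/30)) = 0.1108. Alternative SE = √(0.15 × 0.85/30 + 0.45 × 0.55/45) = 0.0987. Power = Φ((0.30 − 1.96 × 0.1108)/0.0987) = 79.9%; exact enumeration of the Mantel-Haenszel test gives 80.2%. The figure reproduces, but it concerns clinical response. No power is stated for a culture endpoint.

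**2. Where baseline load enters.**

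| Endpoint | Use of baseline load | Adjusted in the test? |
|---|---|---|
| 12.2.9 | Outcome is a fall from the subject's own score | No |
| 12.2.10 | Limited to agar growth at baseline (scores 2 to 6) | No |
| 12.2.11 | None | No |

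**3. Size of chance imbalance at 45 vs 30.** For a standardised load, the SD of the difference in arm means is √(1/45 + 1/30) = 0.236. A gap above 0.25 SD occurs in 29% of trials, above 0.4 SD in 9% and above 0.5 SD in 3%. If 45% of subjects had score 2 or less (assumed), the SD of the difference in that proportion is √(0.45 × 0.55 × (1/45 + 1/30)) = 0.117, and a gap above 10 percentage points occurs in about 39% of trials.

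**4. Effect on the 12.2.11 test.** Simulation with visits at Days 28, 56 and 84, Day 84 conversion of 15% vs 45%, and log-hazard falling by b per SD of load, all assumed. There were 2,500 runs per row.

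| b | Power, planned log-rank | Power, also split by load | Null rejection, planned | Same, when gap > 0.4 SD |
|---|---|---|---|---|
| 0 | 79.1% | 77.3% | 5.1% | 7.1% |
| 0.4 | 77.5% | 78.4% | 4.9% | 4.8% |
| 0.8 | 79.6% | 82.7% | 5.2% | 9.4% |
| 1.2 | 79.7% | 86.6% | 5.3% | 14.0% |

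The last column rests on only about 200 to 230 trials per row, so its Monte Carlo error is roughly 1.5 to 2.3 points; the 7.1% at b = 0 is noise of that kind. Overall error stays near 5%. Error among imbalanced trials rises only when load is strongly prognostic.

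A visit-based hazard model in the same setting (700 runs) had power without and with load of 81.7/81.6, 80.1/81.9, 81.4/88.1 and 81.3/94.1%, a change of about 0 to +13 points.

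**5. The same question on the 0 to 6 score.** Assumed distribution over scores 1 to 6: 15/30/10/10/5/30%. Day 84 conversion was held at 40% vs 71%. At slopes of 0, 0.2, 0.35 and 0.5 per score step, the planned log-rank stays at about 78 to 81%. Adding a load split (2 or less vs 3 or more) gives 78, 80, 86 and 93%. The difference runs from about −2 points at slope 0 to 93 − 81 = +12 at slope 0.5. Between scores 1 and 6, slope 0.5 means a hazard ratio of exp(0.5 × 5) = 12; slope 0.2 means exp(0.2 × 5) = 2.7.

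**6. The other two endpoints.** For 12.2.9, adding a coarse baseline stratum to the CMH test moved power by at most about 1 point either way (72.5 to 71.6, 34.6 to 35.4, 64.5 to 64.1, 35.1 to 34.0%; 4,000 runs each). The simulated placebo chance of a decrease still ran from about 0 at score 1 to about 0.5 at score 5, so the outcome is not free of starting score. No simulation was run for 12.2.10.

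**The case against.** The case for leaving the plan alone has real substance. Efficacy is exploratory, p-values are nominal, and adjusting for the randomisation factor is a legitimate choice. Load by arm and a shift table are already planned, so imbalance would be seen. Under Protocol 8.10, failure to produce sputum after baseline counts as negative, so a negative culture need not reflect a gradual fall in load. Every gain above depends on a slope that the documents do not give. All of this stands, and it limits the point to a supportive analysis. It does not supply an adjusted estimate; the optional subgroups in SAP 11.6 do not either.

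Three stronger readings are tempting but not supported.

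- *All three endpoints ignore load.* They do not adjust for it, but 12.2.9 is defined relative to baseline and 12.2.10 excludes score-1 subjects.
- *The planned tests are invalid.* Overall type I error is intact; the issue is conditional on an imbalance that has arisen.
- *The planned tests lose much of their power.* If the hazard ratio within a load level is fixed at 2.46, planned log-rank power falls from 77% at slope 0 to about 54% at slope 0.5, while a model with the score stays near 78%. But fixing that ratio lets the treatment difference at Day 84 shrink from 32 to 22 points as the slope grows. With Day 84 rates fixed, planned power does not fall. The honest statement is that power is forgone if load is prognostic. None of this was shown for 12.2.9 or 12.2.10.

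**Conclusion.** The point holds as a gap in pre-specification, not as an error in the planned tests. None of the three culture tests adjusts for a baseline measure that the SAP already derives and that randomisation does not balance. It is strongest for 12.2.11.

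For that endpoint, stratifying by load would change power by about −2 to +12 points over slopes of 0 to 0.5 per score step. This rests on the assumed score distribution and on conversion of 40% vs 71%. If load is not prognostic, nothing is gained. For 12.2.9 and 12.2.10 the argument is correction of imbalance only. A gap above 0.4 SD, the size at which the planned log-rank for 12.2.11 was seen to be distorted under strong prognosis, is expected in about 9% of trials.

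**What to change.** Keep the tests in 12.2.9, 12.2.10 and 12.2.11 as they are. Beside them, pre-specify as supportive:

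- for 12.2.11 and 12.2.10, a visit-based (Days 28/56/84) or Cox model;
- for 12.2.9, a logistic model;
- each with treatment, prior antibiotic use and baseline load as one term (score or log CFU), reporting the adjusted treatment effect with a 95% CI.

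If log CFU is chosen, state how 0 CFU/mL is handled, since score 1 has no agar count. Do not add load strata to the log-rank: prior use by two load bands leaves 75/4 ≈ 19 subjects per stratum on average, and prior use by six scores leaves 75/12 ≈ 6. SAP 11.3 already foresees strata too small to use.

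The cost is a few lines of SAP text and a few table rows, with no new data. The model test may be slightly liberal at this size: null rejection was 5.5 to 6.3% in the score-based simulation, and 4.6 to 7.3% with load (5.0 to 6.9% without) in the 700-run one. The interval should therefore carry more weight than the p-value. A single linear term over uneven score bands is a rough fit, accepted because the sample supports little more. If the blind has already been broken, the models can still be run but must be labelled post hoc, as SAP section 6 requires.
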